## **3.4 Participant Retention**

Study participation includes a single study visit either immediately following recruitment or at a later, scheduled date. In extenuating circumstances where a participant is unable to complete all procedures during one visit, a split visit can occur. Details are outlined in Section 4 of the SSP Manual.

## **3.5 Participant Withdrawal**

Participants may voluntarily withdraw from the study for any reason at any point during the study visit. The Investigator of Record (IoR) or designee may also withdraw participants from the study in order to protect their safety and/or if they are unwilling or unable to comply with required study procedures. Participants who withdraw from the study prior to completing the study procedures will be replaced. Study staff will record the reason(s) for all withdrawals from the study in participants’ study records.

### **3.6 Community Definition**

The target venues for recruitment, enrollment, and data collection will be within the surrounding zip codes of the CRS. The protocol team will work with CRSs to select enough zip codes to include a specified number of residents that will allow for rapid enrollment of a representative sampling of the community. Details of the approach and documentation of the final selections will be documented in the SSP Manual.

## **4.0 STUDY PROCEDURES**

An overview of the study visits and procedures is presented in Appendix I. Presented below is additional information on specific study procedures. Additional detailed instructions to guide and standardize all study procedures across sites will be provided in the SSP Manual. Study visits will either take place at the venue, in a location identified by study staff which assures adequate privacy and confidentiality, or at the CRS if an individual is interested in participating but unable to complete the study procedures at that moment. For visits occurring at community venues, tents or privacy screens will be erected to allow for privacy during visit procedures.

Participants will be offered reimbursement for their time and effort via gift cards or other locally developed methods. Measures will be put into place to ensure staff safety in the field, such as gift card activation prior to use.

### **4.1 Informed Consent**

Independent informed consent will be obtained using encrypted electronic tablets from each participant before any study procedures are initiated. If electronic consent is not available, consent can be captured on paper. For more on informed consent, see Section 8.2.

#### **4.1.1 Recruitment and Screening**

Study field teams will consist of recruiters and research assistants, trained in study procedures and specimen collection, who will conduct data and specimen collection at specified venues and times. Recruiters will approach individuals with a brief explanation of the study and invite them to be screened for eligibility. A verbal consent will be administered and then staff will ask their age, if they are already enrolled in this study, and if they are interested in participating.

Individuals will be informed that, in addition to receiving their test results, per local health codes, a positive SARS-CoV-2 diagnostic test result will be transmitted in a confidential manner to local health authorities.

#### **4.1.2 Protocol-Specific Consent Form**

Recruiters will obtain informed consent using encrypted electronic tablets; participants will receive a paper copy of the consent form. A sample protocol-specific consent form is located in Appendix II: Sample Informed Consent Form. (Paper consent may be collected if electronic consent is not available.)

Each CRS is responsible for developing a protocol-specific consent form(s) for local use, based on the sample protocol-specific consent forms in Appendix II: Sample Informed Consent Form. The consent form(s) must be developed in accordance with requirements of the following:

- The single IRB (sIRB)
- CRS's institution, and
- Elements of informed consent as described in Title 45, CFR Part 46 and Title 21 CFR, Part 50, and in ICH E6 (R2), Good Clinical Practice: Consolidated Guidance 4.8.

Study sites are strongly encouraged to have their local Community, Resident or Staff Advisory Board(s) (as appropriate) review their site-specific consent forms. This review should include, but should not be limited to, issues of cultural competence, local language considerations, and the level of understandability.

The sample informed consent form(s) (ICF[s]) include instructions for developing specific content.

## **4.2 Enrollment**

The point of enrollment into this study is when the participant signs the informed consent form.

## **4.3 Questionnaire Administration**

The questionnaire will be administered to each consenting participant (or to the parent of participants up to 9 years of age) using encrypted tablet computers or paper forms. Data collected will include basic demographic, socioeconomic, geographic, clinical, and household SARS-CoV-2 exposure/infection history indicators. (The list of COVID symptoms is included as part of the questionnaire.) A brief knowledge and attitudes questionnaire will be administered to participants aged 10 years or older. Individuals will be asked questions related to personal and community impact from COVID-19, such as loss of employment or housing, and access to basic resources and healthcare. The questionnaire will be tailored for age appropriateness.

## **4.4 Phlebotomy**

A small volume of venous blood ~6 mL for participants aged 2-6 years, ~10 mL for participants aged > 6 years or fingerstick to yield 1mL of blood when staff have unsuccessful attempts at venous puncture (number of failed attempts defined in the SSP), and ~500uL of blood via heel or finger stick (heel stick recommended for participants 2-6 months and finger stick for participants 6 months to 2 years old) will be collected from each participant by trained study staff and labeled with a study ID. Specimens will be kept in a temperature-controlled container at the venue until they are transported to a local laboratory.

Dried blood spots, and plasma or serum aliquots will be prepared at the processing laboratory and stored. Stored samples will be used for serologic testing and will also be stored for specialized SARS-CoV-2 testing. Serologic testing will be performed retrospectively at the LC and/or other centralized network laboratories. The results of these tests will not be returned to study sites or participants.

## **4.5 Nasal Mid-Turbinate Swab Sample Collection**

SARS-CoV-2 RNA testing will be performed on nasal mid-turbinate swab samples for analysis at local laboratories using a testing platform approved by the LC. Procedures for sample collection and processing will be described in the SSP Manual.

## **4.6 Saliva Substudy**

In a subset (approximately 1000) of participants, an additional nasal mid-turbinate swab and saliva will be collected as described in the SSP manual.

#### **4.7 SARS-CoV-2 Counseling**

All study participants will receive counseling messages consistent with the US Center for Disease Control and Prevention (CDC) and local public health authorities. These messages will include instructions on use of masks and how to isolate from others, duration of isolation, how to monitor for worsening of symptoms, and how to connect to social services as needed.

#### **4.8 SARS-CoV-2 Results Reporting**

Participants will be provided with instructions to retrieve the results of their SARS-CoV-2 RNA testing; those with positive test results will receive counseling about isolation and referral to care and will be reminded of plans to inform local health authorities for follow-up and contact tracing. Positive RNA results will be reported to local health authorities as per local health regulations. Serology results are for research purposes only and will not be returned to participants.

#### **4.9 Medical Records Abstraction for Senior Living Facility Participants**

Medical record abstraction will occur for participants who are residents in senior living facilities and who have been consented by their legally authorized representative because of diminished cognitive capacity. Questionnaire domains will include history of chronic illnesses (e.g. diabetes, hypertension, asthma, etc.), smoking history, and prior SARS-CoV-2 diagnosis and will be comparable (when possible) to domains in the questionnaire.

### **5.0 SAFETY MONITORING AND ADVERSE EVENT REPORTING**

As this is an observational study, standard adverse event (AE) reporting will not be undertaken. The study team will monitor for and track serious adverse events (SAEs) related to study procedures and/or to participation in the study. Such events that are unexpected will be reported to the NIAID Medical Officer at the same time as they are reported to IRBs according to pre-established written procedures, as required by 45 CFR 46. This information will not be recorded on case report forms (CRFs) or entered into the study database. Data on social harms will be collected as part of the overall assessment of participant safety.

### **6.0 STATISTICAL CONSIDERATIONS**

#### **6.1 Review of Study Design**

This is a cross-sectional study of individuals residing within the vicinity of selected research sites in the United States who are (i) residing in senior living facilities, (ii) visiting outpatient clinics at given times; and (iii) members of the general population who attend any of the listed community venues at given times. The study aims to estimate prevalence of SARS-CoV-2 infection and IgG seropositivity separately in each of these populations (sampling strategies described above). Given that the three primary endpoints and their respective samples are independent, sites may recruit from one, two, or all three population groups, depending on site capacity (sites must enroll from at least the community venues). Consenting and assenting participants who satisfy the inclusion and exclusion criteria described in Section 3.0, will answer a brief survey and provide a blood sample and nasal mid-turbinate swab(s).

## 6.2 Sample Size

The sample size is calculated for the primary objective, namely, to estimate the seroprevalence of SARS-CoV-2 among individuals and communities where potential COVID-19 vaccine or other prevention interventions studies may be prioritized.

A sample of up to 500 senior living facility residents will be enrolled (described above).

A separate sample of approximately 500 adults from outpatient clinical facilities will be selected according to a TLS design implemented as a two-stage random sample (described above).

The sample size for the TLS sampling was determined based on the minimum sample size needed to achieve prespecified margin of error (MOE). This framework sets a tolerance, also called the margin of error (MOE) for how close we would like the estimated prevalence  $\hat{p}$  to be from the true population prevalence  $p$ . Denoting the MOE by  $e$ , this means

$$Pr(|\hat{p} - p| \leq e) = 1 - \alpha.$$

Assuming  $\hat{p}$  can be treated as normally distributed, this statement is equivalent to setting the half-width of a  $100(1 - \alpha)\%$  two-sided confidence interval to  $e = z_{1-\alpha/2} \sqrt{V(\hat{p})}$  which results in a sample size of

$$n \approx z_{1-\alpha/2}^2 \frac{p(1-p)}{e^2}$$

Table 1 shows the sample sizes needed to achieve required sample sizes with +/-5% and +/-2.5% margin of error on estimated prevalence for a range of assumed prevalence of SARS-CoV-2 antibodies for simple random samples of infinite population size.

**Table 1. Sample Size requirement (per strata) to achieve +/- 5% and +/- 2.5% MOE for a range of assumed seroprevalence**

SARS prev	0.02	0.05	0.1	0.15	0.2	0.25
+/- 5% MOE	30	73	138	196	246	288
+/- 2.5% MOE	120	292	553	784	983	1152

**Table 2. Sample Size requirement (per strata) to achieve +/- 5% and +/- 2.5% MOE for a range of assumed seroprevalence after using a design effect of 2.5.**

SARS prev	0.02	0.05	0.1	0.15	0.2	0.25
+/- 5% MOE	75	182	346	490	615	720
+/- 2.5% MOE	301	730	1383	1959	2459	2881

To estimate the prevalence of infection and seropositivity in each of four age strata (2 months-17, 18-39, 40-59, 60+ years), we assumed the seroprevalence of SARS-CoV-2 may vary from 2.5% to 25%, and specified a margin of error (MOE) of 2.5% for prevalence below 5% and 5% MOE for prevalence between 10 and 25%, and assumed a design effect of 2.5 to account for clustering within social

networks of a venue. These values are shaded in Table 2 above and yield a maximum sample size of 730 per stratum.

### **6.3 Statistical Analyses**

This section briefly describes the final study analyses. Detailed technical specifications of the statistical analyses will be described in a separate Statistical Analysis Plan (SAP).

All statistical analyses will account for the sample design to create the base sampling weights. The sampling weights will be further adjusted for nonresponse and post-stratified using demographic information such as age, sex, race/ethnicity, education, and income. County-level estimates from the census bureau will be used for raking and post-stratification. We will estimate prevalence and calculate 95% confidence intervals of SARS-CoV-2 infection and IgG seropositivity for each target population separately, i.e. among community residents in each of the age groups (2 months-17, 18-39, 40-59, 60+ years); among patients attending the outpatient clinics; and among senior living facility residents.

#### **6.3.1 Primary Analyses**

Design-based estimates using the survey weights will be used to estimate the overall prevalence of SARS-CoV-2 IgG seropositivity among individuals in each of the three target populations. Survey weights will be used to reflect the sampling design for each target population and post-stratified to census data on known demographic variables. Variance of the design-based estimates will be estimated using linearization-based and Jackknife methods. The design-based estimates and corresponding standard errors will be used to construct 95% confidence intervals.

Prevalence estimates in each age group will be estimated using domain estimates implemented as ratio estimates in each subgroup.

Sensitivity analysis may be considered to adjust for test sensitivity and specificity if prevalence is estimated to be lower than 5%.

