## 2.0 STUDY OBJECTIVES AND ENDPOINTS

### 2.1 Primary Objective and Endpoint

Primary Objective	Primary Endpoint
To estimate the prevalence of SARS-CoV-2 IgG seropositivity among individuals in communities surrounding selected NIAID clinical research sites	Proportion of individuals who have SARS-CoV-2 IgG antibodies, evaluated overall and by age strata, in the following populations: 
 
1) Adults 18 and older residing in senior living facilities
 
2) Adults 18 and older attending outpatient healthcare clinics, and
 
3) Individuals in communities of selected research sites in the following age categories               
 
a. 2 months – 17years old
 
b. 18-39 years old
 
c. 40-59 years old
 
d. 60 years and older
 
 
 

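### County census post-stratification is prescribed for all three primary populations, but county residents are the target of only one, so the outpatient-clinic and senior-living estimates do not match their stated endpoints

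*Protocol*

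**What the plan says.** **The targets.** In Section 2.1 the second primary population is "Adults 18 and older attending outpatient healthcare clinics"; the first is adults living in senior living facilities. Section 6.1 describes the clinic group as those "visiting outpatient clinics at given times" and says that the study aims to "estimate prevalence of SARS-CoV-2 infection and IgG seropositivity separately in each of these populations". Section 6.3 lists, apart from community residents by age group, separate estimates "among patients attending the outpatient clinics; and among senior living facility residents". The clinic frame in Section 3.3.2 is a sample of clinic day-times and then of people present. Section 3.3.3 describes the senior living sample as a convenience sample from consenting facilities.

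**The weights.** Section 6.3 opens with a statement about all analyses. It adjusts the weights for nonresponse and post-stratifies them on demographic variables, with age, sex, race/ethnicity, education and income as examples. It then gives one source of control totals: "County-level estimates from the census bureau will be used for raking and post-stratification". Section 6.3.1 covers the primary estimate in each of the three populations, and its weights reflect the design "for each target population and post-stratified to census data on known demographic variables". Section 1.1 says that every prevalence estimate will be weighted so as to represent the communities around the research sites. No control totals specific to clinics or facilities are named anywhere.

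**The concern.** Post-stratification makes a weighted sample match known totals of the population about which one wants to speak. It helps only if the totals describe that population. County census margins suit the community-venue sample. They do not describe people who attend the listed clinics or live in the participating facilities.

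Forcing a clinic sample to county margins replaces the attendees' own demographic mix with the county's. The result is not prevalence among attendees, because their mix has been removed. Nor is it prevalence in the county, because every respondent still attends a clinic. The same reasoning applies to facility residents.

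Two of the three primary estimates would therefore answer a question other than the one in Section 2.1. Any discrepancy is systematic: it does not shrink with sample size, and the confidence interval does not reflect it.

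**Working it through.** **The plan's own figure.** Section 6.2 uses n = z² p(1 − p)/e², multiplied by the design effect. With z = 1.96, p = 0.05, e = 0.025 and design effect 2.5, n = 729.9, which matches the 730 in Table 2. All 24 cells of Tables 1 and 2 reproduce. The sample-size arithmetic is sound and is not at issue.

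**Half-width for scale.** With n = 500 (Section 6.2) and design effect 2.5 (stated for the venue age strata, assumed here for clinics):

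1.96 × √(2.5 × 0.15 × 0.85 / 500) = 4.95 points at 15% prevalence. The same formula gives 2.2 points at 2.5%, 4.2 at 10% and 6.0 at 25%.

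**Effect of the weighting.** The protocol gives no demographic mix for clinics or counties, so all mixes below are assumptions, and age is the only variable used. County adults are taken as 38/33/29% aged 18–39/40–59/60+. Age-specific seroprevalence stays within the 2.5% to 25% range of Section 6.2.

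- Stated target = Σ (clinic share × age-specific prevalence)
- Post-stratified estimate = Σ (county share × age-specific prevalence)

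| Clinic mix, % | Seroprevalence by age, % | Stated target, % | After county weighting, % | Shift, points |
|---|---|---|---|---|
| 38/33/29 (as county) | 25/10/2.5 | 13.525 | 13.525 | 0 |
| 15/30/55 | 10/10/10 | 10.00 | 10.00 | 0 |
| 30/33/37 | 15/10/5 | 9.65 | 10.45 | +0.8 |
| 30/33/37 | 25/10/2.5 | 11.725 | 13.525 | +1.8 |
| 15/30/55 | 25/10/2.5 | 8.125 | 13.525 | +5.4 |
| 30/33/37 | 5/10/15 | 10.35 | 9.55 | −0.8 |
| 15/30/55 | 2.5/10/25 | 17.125 | 11.50 | −5.6 |

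Worked for the +5.4 row:
- target: 0.15 × 25 + 0.30 × 10 + 0.55 × 2.5 = 3.75 + 3.00 + 1.375 = 8.125
- weighted: 0.38 × 25 + 0.33 × 10 + 0.29 × 2.5 = 9.50 + 3.30 + 0.725 = 13.525

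The half-width at 8.125% is 3.8 points and at 17.125% is 5.2 points, so in the two extreme rows the shift exceeds the planned half-width. In the mild rows it is well inside it.

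**Variance cost.** The Kish factor is Σ (county share² / clinic share). For the 15/30/55 mix it is 0.1444/0.15 + 0.1089/0.30 + 0.0841/0.55 = 1.48, so 500 becomes about 338 before clustering. For the 30/33/37 mix it is 1.04, or about 481. This is an approximation that ignores any precision gained by calibration.

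**Senior living sample.** No mix is given here either. Each weight is county share divided by sample share, so it grows without limit as an age band becomes rare among residents, and a band with no residents cannot be matched to the county at all.

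**The case against.** The best defence is that the text is looser than it looks. In Section 6.3.1 the words about each target population grammatically qualify the sampling design, the variable list in Section 6.3 is only illustrative, and technical detail is left to the SAP. This does not remove the problem. Section 6.3 opens with all analyses, Section 6.3.1 covers all three populations, and the protocol itself fixes the census as the control source. A SAP that used other controls for clinics would depart from that text.

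A second defence is that standardising to the community is deliberate: Section 1.1 states that aim, and the primary objective speaks of communities around the sites. That is a coherent purpose, and a census-standardised clinic figure can be reported. It is a different estimand from endpoint 2, however, and the protocol nowhere says that it replaces it. Sections 1.1, 2.1, 6.1 and 6.3 need to be reconciled. Nonresponse is no justification, since Section 6.3 adjusts for it as a separate step.

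It also stands that nothing irreversible is at stake. The weights are computed after collection, and neither enrolment nor sample size changes.

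Four stronger readings are tempting but unsupported:
- **That the county is younger and healthier, so the clinic estimate is pushed upward.** The protocol says nothing about either mix, and health is not a listed weighting variable. The direction is unknown.
- **That only the clinic sample is affected.** The same wording reaches senior living residents.
- **That Secondary Objective 5 totals from clinic weights would be county totals.** Section 6.3.2 does not say which sample supplies those totals, and raking can use proportions without scaling to county counts.
- **That calibrating to clinic visit counts would cure it.** The endpoint is a proportion of individuals; raw visits over-represent frequent attenders.

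**Conclusion.** The protocol contradicts itself on a primary analysis. As written, the weighting for the clinic and senior living populations targets those groups standardised to county demographics, while Sections 2.1, 6.1 and 6.3 ask for prevalence in the groups themselves. This conclusion rests on the text alone and needs no assumed figure.

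The size does rest on assumptions. Under the assumed age mixes and gradients the clinic estimate shifts by 0 to about 5 points in either direction, against a half-width of about 5 points at 15% prevalence. The shift is zero if the mixes agree or if prevalence is flat across the weighting variables. Variables other than age could add to it or offset it. The inconsistency is certain; the size and sign of the resulting bias are not.

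**What to change.** - **Sections 6.3 and 6.3.1, and the weighting statement in Section 1.1:** limit census raking and post-stratification to the community-venue sample.
- **Clinics:** use the time-location design weights with nonresponse adjustment. If calibration is wanted, calibrate to the demographic mix of individual attendees at the listed clinics, with attendance frequency accounted for, and not to raw visit counts.
- **Senior living facilities:** if calibration is wanted, use the participating facilities' own resident mix.
- **If a census-standardised clinic figure is intended:** state that estimand and report the unstandardised estimate beside it.
- **Secondary Objective 5:** state which sample's weights produce the population totals.

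The cost is wording in the protocol and matching text in the SAP, with no change to enrolment, sample size or assays. Optional calibration would need aggregate attendee or resident demographics from the participating clinics and facilities, and information on attendance frequency for clinics.

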### **7.3 Endpoint Assays**

For SARS-CoV-2 infection, RNA testing will be performed using nasal mid-turbinate swabs at local or clinical reference laboratories using a laboratory platform approved by the LC.

For SARS-CoV-2 seroprevalence, SARS-CoV-2 specific IgG antibodies will be evaluated in centralized laboratories approved by the LC using assays that are Food and Drug Administration (FDA)-approved or have Emergency Use Authorization (EUA) from the US FDA. The SARS-CoV-2 specific IgG antibody assay employed will target the viral nucleocapsid protein.

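### Correction for assay sensitivity and specificity is optional and tied to an uncorrected estimate below 5%, leaving out most of the protocol's 2.5–25% planning range

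*Protocol*

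**What the plan says.** The primary endpoint in Section 2.1 is the "Proportion of individuals who have SARS-CoV-2 IgG antibodies, evaluated overall and by age strata, in the following populations": senior living residents, outpatient clinic attendees and community members.

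Section 6.3.1 estimates these proportions with survey weights and then says "The design-based estimates and corresponding standard errors will be used to construct 95% confidence intervals". Nothing in that estimator corrects for test error. The only provision is: "Sensitivity analysis may be considered to adjust for test sensitivity and specificity if prevalence is estimated to be lower than 5"%.

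In Section 6.2, "we assumed the seroprevalence of SARS-CoV-2 may vary from 2.5% to 25"%, and the planners "specified a margin of error (MOE) of 2.5% for prevalence below 5% and 5% MOE for prevalence between 10 and 25"%. They "assumed a design effect of 2.5 to account for clustering within social" networks at a venue. The shaded values in Table 2 "yield a maximum sample size of 730 per stratum".

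Section 7.3 requires an IgG assay against the nucleocapsid protein, chosen from "assays that are Food and Drug Administration (FDA)-approved or have Emergency Use Authorization (EUA) from the US FDA". No sensitivity or specificity is stated. Section 6.3.2 keeps the test-performance estimates within the saliva substudy and does not link them to the prevalence estimates.

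**The concern.** The endpoint is the share of people who truly have IgG antibodies. A positive assay result is an imperfect reading of that, and the error has two parts with opposite signs. False positives add (1−Sp)(1−p). False negatives subtract (1−Se)p. The first weighs most in relative terms when prevalence is low, which is presumably why a 5% trigger was chosen. In percentage points, though, it hardly changes as prevalence passes 5%, and the second part increases steadily toward 25%. The cutoff therefore leaves no provision where the sensitivity error is largest.

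The condition is also applied to the estimate that contains the error. False positives can lift a true prevalence below 5% over the line, so the adjustment is not prompted where it was meant to apply. Two strata or sites reading 4.9% and 5.1% could be reported on different footings by chance.

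Secondary Objective 5 extrapolates design-based estimates to population sizes for referral, and Section 1.1 says the results will guide site selection and participant allocation in later studies. A bias in the proportion carries into both.

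**Working it through.** **Inputs from the protocol.** Section 6.2: planning range 2.5–25%, margins of error 2.5 and 5 points, design effect 2.5, n = 730 per stratum (Schema: 4 × 730 = 2,920 per site). Section 6.3.1: 95% intervals.

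**Assumed inputs.** Se 0.90 or 0.95 and Sp 0.98 or 0.995. The protocol gives neither, so all four pairs are shown.

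**The plan's own figure.** n = 2.5 × 1.96² × 0.05 × 0.95 / 0.025² = 729.9. The stated 730 is reproduced.

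**Share of the range outside the provision.** (25 − 5) / (25 − 2.5) = 20/22.5 = 89% of the width. This is not a probability that estimates will fall there.

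**Formulas.** Expected reading a = p·Se + (1−p)(1−Sp). Bias = a − p. SE = √(2.5·a(1−a)/n). Coverage of the uncorrected 95% interval = P(|Z + bias/SE| < 1.96).

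Worked example, Se 0.90, Sp 0.995, p = 25%: a = 0.25 × 0.90 + 0.75 × 0.005 = 0.2288; bias −2.12 points; SE = √(2.5 × 0.2288 × 0.7712 / 730) = 2.46 points; coverage 86%.

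Stratum bias in points, with coverage, n = 730:

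| Se / Sp | p = 2.5% | p = 5% | p = 10% | p = 25% |
|---|---|---|---|---|
| 0.95 / 0.995 | +0.36 (93%) | +0.23 (95%) | −0.05 (95%) | −0.88 (94%) |
| 0.90 / 0.995 | +0.24 (94%) | −0.02 (95%) | −0.55 (94%) | −2.12 (86%) |
| 0.95 / 0.98 | +1.83 (67%) | +1.65 (80%) | +1.30 (89%) | +0.25 (95%) |
| 0.90 / 0.98 | +1.70 (70%) | +1.40 (84%) | +0.80 (93%) | −1.00 (93%) |

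The 2.5% column mostly lies inside the trigger region, so it shows the cost of making the analysis optional. The other columns bear on the cutoff.

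The two errors cancel at p = (1−Sp)/(2−Se−Sp): 9.1%, 4.8%, 28.6% and 16.7% for the four rows in order. The sign therefore depends on the assay.

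**Whole-site community estimate, n = 2,920.** If a design effect of 2.5 also holds for the pooled sample:

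- Se 0.90 / Sp 0.995 at 25%: SE 1.23 points, coverage 59% (39–77% for pooled design effects of 1.5–5).
- Se 0.95 / Sp 0.98 at 10%: SE 0.93 points, coverage 71% (56–83% over the same span).

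**The trigger, read at stratum level.** P(estimate < 5%) = Φ((0.05 − a)/SE). The true prevalence at which the average reading is exactly 5% is (0.05 − (1−Sp))/(Se + Sp − 1).

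- Se 0.95 / Sp 0.98: this is 0.03/0.93 = 3.2%. A stratum at true 4% reads 5.7% on average (SE 1.36 points) and meets the condition about 30% of the time, although its bias is +1.7 points. At true 5% it reads 6.65% and meets it about 13% of the time.
- Se 0.90 / Sp 0.995: a stratum at true 5% reads 4.98% and meets the condition about 51% of the time.

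**The case against.** The strongest reply is that Section 6.3 is only a summary, with technical detail deferred to a statistical analysis plan that is not shown, and that the sentence is permissive: it does not forbid adjustment at 5% or above. That is true, and the analysis plan may do better. But the protocol is not silent here. It names a condition and an optional status, and adjustment above 5% would then be a choice made after the estimate is known.

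Second, the harm depends on unseen assay performance. At 10% and 25%, six of the eight cells in the table have coverage of 93–95%, and the largest bias, 2.1 points, is under half the planned 5-point margin. With Se 0.95 and Sp 0.995 the effect at stratum level is negligible. This stands as a limit on size. It does not rescue the rule, because the protocol cannot know in advance which row applies. Section 7.3 narrows the assay to a nucleocapsid target and a regulatory status but sets no performance, and Sections 4.4 and 7.1 allow venous, capillary and dried-blood-spot specimens.

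Third, the objective speaks of IgG seropositivity, for which the proportion testing positive is a defensible measure. That supports keeping the uncorrected figure. Yet the endpoint refers to people who have antibodies, and providing for any adjustment accepts true status as the target.

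Fourth, the site-level coverages need an assumed pooled design effect, and the protocol does not say whether the trigger is read by stratum, site or population. Both caveats stand. The second is a further ambiguity in the rule.

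**Conclusion.** The concern holds and should be fixed. The only provision for test error is discretionary and conditioned on an uncorrected estimate below 5%, against a planning range that lies mostly above that point. For the Se and Sp pairs examined, stratum bias at 5–25% runs from about −2.1 to +1.65 points, with coverage of nominal 95% intervals between 80% and 95%. The whole-site estimate is more exposed because its standard error is smaller. These figures rest on assumed Se and Sp, the protocol's design effect of 2.5 and a normal approximation. Neither the direction nor the size of the bias can be known until the assay's performance is. The uncorrected analysis remains valid as an estimate of the proportion testing positive; it is incomplete as an estimate of the stated endpoint.

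**What to change.** In Section 6.3.1, remove the optional wording and the 5% condition. State that for every target population and age stratum, at any prevalence, the survey-weighted prevalence corrected for assay sensitivity and specificity will be reported beside the uncorrected proportion. Use the Rogan-Gladen estimator, (a + Sp − 1)/(Se + Sp − 1), or an equivalent. Carry the uncertainty in Se and Sp into the 95% interval, and use specimen-specific values where validation data exist. Name the source of Se and Sp in the analysis plan.

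The cost is wording in the protocol and analysis plan, plus use of assay validation data. Sampling, sample size and specimens do not change. The corrected interval widens by about 1/(Se + Sp − 1), before uncertainty in Se and Sp is added:

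- Stratum at 25%: half-width from 4.9 to 5.2 points (Se 0.95, Sp 0.995) or from 4.8 to 5.4 (Se 0.90, Sp 0.995), slightly over the 5-point target.
- Stratum at 10%: from 3.6 to 3.9 points (Se 0.95, Sp 0.98).

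Poor Se or Sp inputs would bring their own error, which is the reason to show both estimates.
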